10.2. Infusions with One or More Temporally Associated AEs

The number of infusions with at least one temporally associated adverse event (including AEs judged not to be related to *CUTAQUIG* by the investigator) over the total number of infusions will be calculated for each patient, and the ratio will be presented, including the associated upper one-sided 95% confidence limit. The calculation of this confidence interval will take into account the observed intra-patient correlation - this is necessary because each patient may experience more than one infusion with an associated AE; it can therefore not be assumed that the observed events are statistically independent.

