If adverse drug reactions (ADRs) occur during an infusion, the patient may go back to the previous regimen that was tolerated if deemed necessary by the Investigator and/or patient; this would include reintroducing an injection site. This infusion regimen will continue until the next study visit at which the patient would again attempt to remove an injection site. If ADRs occur again, the patient may again go back to the previous stable regimen if deemed necessary until the next study visit. Following

unsuccessful attempts to increase volume, the Investigator and patient can cease or hold additional attempts and remain in the study; however, every effort to increase injection site volumes should be attempted.

Optional: When modifying the number of injection sites after previous unsuccessful attempts, the Investigator can make adjustments to lower the flow rate. This may include decreasing pump flow rate, revising the tubing, or changing needle gauge.

Note: Sites are encouraged to enroll patients into Cohort 1 who are already on a dosing regimen using at least 3 infusion sites to ensure that volume increases remain below limits listed in Table 6. Patients dosing with 1 infusion site cannot enter Cohort 1.

Cohort 2 (increased infusion rate - patients will receive CUTAQUIG weekly and increase infusion rates every 4 weeks): Patients will return to the clinic for the Treatment Period Baseline Visit, at which they will receive the same body-weight dependent (mg/kg) dose of CUTAQUIG but the infusion rate per site will be increased by up to a maximum allowed flow rate increase per infusion site of 25 mL/hr/site for patients ≥ 40 kg or 10 mL/hr/site for patients < 40 kg. Patients will receive this new flow rate for 4 weekly infusions (Treatment Period Baseline and Weeks 1, 2, and 3), and return to the clinic at Week 4 for their next infusion at an increased infusion rate. This cycle will continue, with maximum allowed flow rate increases per infusion site of up to 25 mL/hr/site for patients ≥ 40 kg or 10 mL/hr/site for patients < 40 kg every 4th infusion until reaching either 1) a maximum flow rate (100 mL/hr/site) or the maximum flow rate achievable by the pump, or 2) the maximum tolerated flow rate (maximum flow rate based on Investigator's decision of patient's tolerance) – whichever is reached first.

The following rate increases should be followed:

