3.1. Study Objectives

3.1.1. Primary Objectives

The co-primary objectives of this study are to assess CUTAQUIG administered using the following infusion parameters:

- Compare total IgG trough levels from weekly infusions to every other week infusions
- Safety and tolerability when administered at increased infusion volumes at each infusion site
- Safety and tolerability when administered at increased infusion flow rates at each infusion site
- Safety and tolerability when administered on an every other week dosing regimen

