7.4. Derived and Computed Variables

The following derived and computed variables have been initially identified as important for the analysis of the primary and secondary target variables. It is expected that additional variables will be required. The SAP will not be amended for additional variables that are not related to the primary target or key secondary target variables. Any additional derived or computed variables will be 090-SAP-SCGAM-06-clean version3.0_13FEB2022

identified and documented in the SAS programs that create the analysis files. If the SAP is not amended, further derivations related to primary and secondary target variables will be described in the CSR.

- **Age** will be derived according to the usual definition that a person is n years old until she or he has completed her or his $(n+1)^{\text{th}}$ year of life, using the date of informed consent as the reference date. This is also the definition that will be applied for evaluation of the age related inclusion criteria [Unit: years]
- **Body Mass Index:** $\text{BMI} = (\text{Body weight}) / \text{Height}^2$ [Unit: kg/m^2]
- The **CUTAQUIG stabilization period** is defined for patients that did not participate in the SCGAM-03 trial as the period between the day of first treatment with study drug to the end of the observation period. This will usually be the treatment period baseline visit.
- The **CUTAQUIG treatment period** is defined as the period between the day of first treatment with study drug in a modified dosing regimen to the end of the observation period. For patients that previously completed the SCGAM-03 trial, this is also the period of first treatment with the SCGAM-06 study drug. The end of the observation period will usually be the termination visit.
- The **rate of serious bacterial infections** per year during regularly repeated treatment with CUTAQUIG will be calculated as $r = (\text{Total number of serious bacterial infections occurring in the stabilization and treatment periods}) / (\text{Sum of stabilization and treatment periods})$ [Unit: 1/years]
- The **rate of other infections** will be derived using the same method

Calculation of the confidence intervals of these rates will account for intra-patient correlation in incidents following a compound Poisson process model.[1]

With C_i infections for the i^{th} patient, and C total infections, the adjusted 2-sided 98% CI is calculated by:

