$$\left[e^{\ln(r) - 2.33 \cdot \sqrt{\frac{\sum C_i^2}{C^2}}} ; e^{\ln(r) + 2.33 \cdot \sqrt{\frac{\sum C_i^2}{C^2}}} \right]$$

If there are 0 infections, an alternative method will be used to approximate the upper bound on the 98% confidence interval using a chi-square distribution and the following SAS code:

```
data poisson;
events=0;
sumyrs=xxx;
ul=cinv(0.99,2*(events+1))/2;
rate=events/sumyrs;
ulinc=ul/sumyrs;
run;
where
sumyrs = duration of treatment in years
events = total number of events
```

rate = total number of events per person-year

ulinc = two-sided 98% CI - upper limit

- The **rate of infusions with one or more temporally associated AEs** will be calculated for each patient as $r = (\text{Number of infusions with one or more temporally associated AEs}) / (\text{Number of infusions started})$. An AE is defined as a temporally associated if, and only if, the onset (or worsening) is either during an infusion of study medication or within 72 hours of the end of the infusion. [Unit: N/A]

Property of Octapharma. Do not copy or distribute without written permission.

8. Study Subjects and Demographics

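### The per-infusion AE ratio in SAP 10.2 pools raised-level infusions with Stabilization and stepped-back infusions, so it can understate AE risk at the increased volume or flow rate

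*SAP*

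**What the plan says.** **The ratio.** SAP 10.2 takes the number of infusions with at least one temporally associated AE, related or not. This number "over the total number of infusions will be calculated for each patient, and the ratio will be presented". The result comes with a limit ("including the associated upper one-sided 95% confidence limit"), which is to allow for correlation within patients. SAP 7.4 defines the same rate with the denominator "Number of infusions started". Neither section restricts the denominator by period, volume or rate. SAP 7 asks for summaries overall and by cohort.

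**The objective.** One co-primary objective in SAP 3.1.1 reads "Safety and tolerability when administered at increased infusion volumes at each infusion site". A parallel objective covers increased flow rates.

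**Step-back.** Under protocol 3.3.2, after an adverse drug reaction in Cohort 1 or 2, "the patient may go back to the previous regimen that was tolerated if deemed necessary by the Investigator and/or patient". That regimen runs until the next visit, when a new attempt is expected. After unsuccessful attempts in Cohort 1, "the Investigator and patient can cease or hold additional attempts and remain in the study". Cohort 2 has an equivalent sentence.

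**The period.** SAP 7.4 says of the Treatment Period that it "is defined as the period between the day of first treatment with study drug in a modified dosing regimen to the end", meaning until observation stops. Stepped-back infusions therefore lie inside it.

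**Other planned outputs.** SAP 10.1 plans patient counts of temporally associated events by period. It also plans tables by total infusion flow rate, and a table by flow rate over number of lines for local reactions only. It states no infusion denominator for the flow-rate tables and names no output by volume per site. The detailed table list is deferred to a separate document.

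**The concern.** In Cohorts 1 and 2, exposure to the raised level depends on the outcome. A reaction can move the patient to a lower level, and the infusions given there stay in the denominator. Infusions at the pre-study volume or rate carry no information on tolerability above it. If the raised level has the higher AE rate, those infusions pull the ratio down. The four Stabilization infusions do the same for every patient who did not roll over directly from SCGAM-03. Allowing for intra-patient correlation widens the limit but does not remove this shift, and a split by period would remove only the Stabilization part. At stake is whether the Cohort 1 and 2 tolerability objectives have a per-infusion figure that matches their wording.

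**Working it through.** The documents give no expected value, threshold or sample size for this ratio, so there is no planned figure to reproduce.

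**Inputs from the documents**
- Stabilization: 4 infusions (protocol Study Outline); none for direct SCGAM-03 rollovers.
- Treatment Period: weekly, Baseline to Week 24 inclusive = 25 infusions (protocol Tables 2 and 3). Total 4 + 25 = 29.
- Scheduled increases: Baseline and Weeks 4, 8, 12, 16 and 20 = six attempts (protocol 3.3.2).
- At least 15 patients in each of Cohorts 1 and 2 (protocol 9.1).

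**Assumptions (the documents give no AE rates)**
- 5 of 15 patients are intolerant, with AE probability 0.60 per raised infusion.
- The AE probability is 0.05 for all other infusions.
- An intolerant patient steps back to the pre-study level after an AE and stays there until the next attempt.
- The other 10 patients stay at the raised level throughout.
- Mean risk per raised infusion is then (5 × 0.60 + 10 × 0.05)/15 = 23.3%.

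**One patient.** A patient reacts at the first raised infusion, steps back, makes no further attempt and has no other AE. The result is 1/29 = 3.4% (1/25 = 4% for a rollover), although 1 of 1 raised infusions had an AE.

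**Cohort, one attempt, Treatment Period only**
- Raised infusions per intolerant patient: 1/0.60 = 1.667, ending in 1 AE.
- Old-level infusions: 25 − 1.667 = 23.333, with 23.333 × 0.05 = 1.167 AEs.
- Intolerant ratio: (1 + 1.167)/25 = 8.67%. Tolerant ratio: 5%.
- All infusions: (5 × 8.67% + 10 × 5%)/15 = **6.2%**. Pooled and mean-patient versions agree because every patient has 25 infusions.
- Raised only, pooled: (5 + 250 × 0.05)/(5 × 1.667 + 250) = 17.5/258.3 = **6.8%**.
- Raised only, mean of patient ratios: with N the number of raised infusions, an intolerant patient's expected ratio is E(1/N) = 0.6 × ln(1/0.6)/0.4 = 0.766. The mean is (5 × 0.766 + 10 × 0.05)/15 = **28.9%**.
- Old-level share of infusions: 5 × 23.333/375 = 31%.

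**Cohort, six attempts, Treatment Period only**
- Raised infusions per intolerant patient: five blocks of (1 − 0.4⁴)/0.6 = 1.624 and a last block of (1 − 0.4⁵)/0.6 = 1.650, in total 9.770.
- AEs: 0.6 × 9.770 = 5.862 raised, and 15.230 × 0.05 = 0.762 old level. Ratio: 6.624/25 = 26.5%.
- All infusions: (5 × 26.5% + 10 × 5%)/15 = **12.2%**.
- Raised only, pooled: (5 × 5.862 + 12.5)/(5 × 9.770 + 250) = 41.8/298.8 = **14.0%**.
- Raised only, mean of patient ratios (simulation, 4,000 runs): **24.5%**.
- Old-level share: 5 × 15.230/375 = 20%.

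**Adding the Stabilization infusions** (4 × 0.05 = 0.2 AEs per patient)
- One attempt: an intolerant patient has 2.367/29 = 8.16%, and the cohort (5 × 8.16% + 10 × 5%)/15 = 6.1%.
- Six attempts: 6.824/29 = 23.5%, and the cohort 11.2%.

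**Other assumptions.** Let intolerant patients react to every raised infusion and stop after two attempts, with an old-level rate of 5% and 29 infusions. An intolerant patient then has (2 + 27 × 0.05)/29 = 11.6%.
- 3 of 15 intolerant, others at 5% when raised: all infusions (12 × 5% + 3 × 11.6%)/15 = 6.3%; raised pooled 21/306 = 6.9%.
- 8 of 15 intolerant, others at 20% when raised, so (5 + 0.2)/29 = 17.9% each: all infusions (7 × 17.9% + 8 × 11.6%)/15 = 14.5%; raised pooled 51/191 = 26.7%.

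**The case against.** Much of the case on the other side stands.

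- **The ratio is not decisive.** It is not among the primary target variables in SAP 3.2.1 and carries no threshold. Patient counts by period cannot be diluted in this way, because a patient who reacts once counts fully. The flow-rate tables cover Cohort 2 in part. As a description of titration to tolerance, the all-infusions ratio is legitimate.
- **The extreme case is not what the protocol expects.** Step-back is optional, re-attempts are expected, and stopping follows unsuccessful attempts. After a later failure, the previous tolerated regimen can still be above the pre-study level.

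A reader might also infer two stronger claims, which the documents and the arithmetic do not support.

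- **That the least tolerant patients add the most AE-free infusions.** In the illustration a tolerant patient has 25 × 0.95 = 23.75 AE-free Treatment Period infusions. An intolerant one has 25 − 2.167 = 22.8 (one attempt) or 25 − 6.624 = 18.4 (six attempts). The ratio still ranks intolerant patients as worse: 8.7% or 26.5% against 5%. They add more AE-free infusions than they would have at the raised level, and no more than that follows.
- **That stepped-back infusions alone explain 6% against 29%.** Like for like, the pooled contrast is 6.2% against 6.8%. The rest arises because a mean of patient ratios gives a patient with one or two raised infusions the same weight as one with 25. SAP 10.2 calculates per patient, while SAP 10.1 also lists a percentage of infusions, so the SAP does not settle which weighting applies.

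**Conclusion.** The point holds in a limited form. The denominator is unrestricted, step-back is permitted, and the ratio and its upper limit understate per-infusion AE risk at the increased volume or rate whenever that risk exceeds the risk at the old level. If the two risks are equal, there is no bias.

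Under the main assumptions the pooled shortfall is 0.6 to 1.8 percentage points over the Treatment Period. It reaches 12.2 points (14.5% against 26.7%) when about half the cohort is intolerant and Stabilization is included. On a mean-patient basis it is 22.7 points (one attempt) or 12.3 points (six attempts) in the main illustration. All of these rest on assumed AE rates.

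The gap matters most for Cohort 1, because the SAP names no output by volume per site. This is an inexpensive improvement to a supportive output. It does not invalidate the tolerability analysis.

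**What to change.** In SAP 7.4 and 10.2:

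1. Keep the all-infusions ratio, labelled as describing the whole titrate-to-tolerance course, Stabilization included.
2. Beside it, for Cohorts 1 and 2, report the ratio and its upper limit separately for infusions above, and for infusions at or below, the patient's last pre-Baseline level.
3. Define the level as the largest volume given at any single site (Cohort 1) or the flow rate per site (Cohort 2). Total dose over number of sites would fail on the protocol's own example. When 30 + 30 mL becomes 50 + 10 mL, that quotient stays at 30 mL, while the largest single-site volume rises from 30 to 50 mL.
4. Do not count a change due only to weight-based dose adjustment as a step.
5. Show pooled and mean-patient versions, and the number of patients who stepped back or ceased attempts.

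**Cost.** SAP wording and one derived flag. SAP 8.4 already plans to summarize injection sites, flow rates and volumes. The documents do not say whether volume at each site is recorded when the split is unequal, so the eCRF should be checked.

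**Downside.** The above-level ratio rests on fewer infusions, and its mean-patient version runs high when patients stop at their first reaction (28.9% against 23.3% in the illustration). A patient who returns from a second step to a first one still counts as above. The split should therefore sit beside the all-infusions ratio and not replace it.

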10.3. Clinical Laboratory Evaluations

The following laboratory tests will be performed during the course of the study to investigate the safety and tolerability of *CUTAQUIG*; for the timing of these lab panels and tests please refer to section 7.3.4 (Laboratory Tests) of the protocol:

- Standard hematology
 - Complete blood count [CBC]

- WBC differential
- Hematocrit
- Hemoglobin
- Clinical chemistry
 - Sodium
 - Potassium
 - Glucose
 - Alanine aminotransferase [ALAT]
 - Aspartate aminotransferase [AST]
 - Lactate dehydrogenase [LDH]
 - Total bilirubin
 - Blood urea nitrogen or blood urea creatinine
- Urinalysis
 - pH
 - Glucose
 - Ketones
 - Leukocytes
 - Hemoglobin
 - Urine pregnancy test (women of childbearing potential)

All laboratory assessments will be done at the local laboratories according to the site's standard procedures.

Total serum IgG trough levels will be determined by central laboratories.

All laboratory data will be converted to standard units during the Data Management process. The laboratory data will be listed with suitable flags indicating abnormal values (L=Lower than reference range, H=Higher than reference range).

Summary statistics for the laboratory values as well as their changes from baseline at each time will be tabulated for all laboratory parameters.

10.4. Vital Signs

To evaluate short-term tolerance, monitoring of vital signs including blood pressure, body temperature, pulse and respiratory rate will be performed at visits taking place at the clinic/study site according to the flow chart of assessments provided in study outline.

Measurements will be carried out before the infusion of IMP.

Vital signs parameters will be summarized by visit and measurement time, using the standard set of summary statistics for both absolute values and changes from baseline, where the baseline value is the pre-infusion measurement.

10.5. Further Safety Evaluations

10.5.1. Physical Examination

A general physical examination will be performed at the Screening Visit according to routine procedures and will be as comprehensive as necessary to detect relevant abnormalities. If any findings are abnormal, the Investigator will document the start date and whether or not the abnormal finding is still present at the start of treatment. The physical examination will be repeated at subsequent study

visits (at 12 week intervals), and finally at the Termination Visit (irrespective of whether termination is regular or premature). Clinically relevant worsening from the status at screening will be documented as an AE. Summary counts of patients with clinically significant abnormalities will be presented by visit.

Property of Octapharma. Do not copy or distribute without written permission.

11. Reporting Conventions

The following reporting conventions will be adopted for the presentation of study data. These conventions will enhance the review process and help to standardize presentation with common notations.

11.1. General Reporting Conventions

- All tables and data listings will be developed in landscape orientation, unless presented as part of the text in a CSR.
- Figures will in general also be presented in landscape orientation, unless presented as part of the text in a CSR. Exceptions are the Trellis plots that will be presented in portrait orientation.
- Legends will be used for all figures with more than one variable or item displayed.
- Figures will be in black and white, unless color figures have been identified as useful for discriminating presentation in the figure. Lines in figures should be wide enough to view the line after being photocopied.
- Specialized text styles, such as bolding, italics, borders, shading, superscripted and subscripted text will not be used in tables, figures and data listings unless they add significant value to the table, figure, or data listing.
- Only standard keyboard characters should be used in tables and data listings. Special characters, such as non-printable control characters, printer specific, or font specific characters, will not be used on a table, figure, or data listing. Hexadecimal character representations are allowed (e.g., μ , α , β).
- The ICH numbering convention is to be used for all tables, figures and data listings.
- All footnotes will be left justified and placed at the bottom of a page. Footnotes must be present on the page where they are first referenced. Footnotes should be used sparingly and must add value to the table, figure, or data listing. If more than four footnote lines are planned then a cover page may be used to display footnotes.
- Missing values for both numeric and character variables will be presented as blanks in a table or data listing. A zero (0) may be used if appropriate to identify when the frequency of a variable is not observed.
- All date values will be presented as DDMMYYYY (e.g., 29AUG2001) format.
- All observed time values will be presented using a 24-hour clock HH:MM format (e.g. 15:26).
- Time durations will be reported in HH:MM notation. The use of decimal notation to present (display) time durations should be avoided (e.g. 0.083h = 5min) unless it is necessary to show the computation of time differences in a table, figure, or data listing, in which case both notations may be used to display the time duration.
- All tables, figures and data listings will have the name of the program, and a date stamp on the bottom of each output.

11.2. Population Summary Conventions

- Population(s) represented on the tables or data listings will be clearly identified in the title as "Population: <name of population>" where <name of population> is any of the analysis population names or abbreviations defined in section 6 (safety analysis set (SAF), full analysis set (FAS or ITT), per-protocol set (PP)).

- Sub-population(s) or special population(s) descriptions will provide sufficient detail to ensure comprehension of the population (e.g., ITT Females, Per-Protocol Males >60 years of age) used for analysis in a table or figure.
- Population sizes may be presented for each treatment or dosing category as totals in the column header as (N=xxx), where appropriate.
- Population sizes shown with summary statistics are the samples sizes (n) of patients with non-missing values.
- All population summaries for continuous variables will include: N, mean, SD, median, Q1, Q3, minimum and maximum.
- All percentages are rounded and reported to a single decimal point (xx.x%).

Property of Octapharma. Do not copy or distribute without written permission.

12. References

- [1] Kegler SR (2007) Applying the compound Poisson process model to the reporting of injury-related mortality rates. *Epidemiologic Perspectives & Innovations* 2007, 4:1

Property of Octapharma. Do not copy or distribute without written permission.

13. Tables, Listings and Figures

To be supplied in a separate document later when all feedback from authorities will be available.

Property of Octapharma. Do not copy or distribute without written permission.
